11.3. Analysis Datasets

The safety population will consist of all subjects receiving the OTX-TIC implant. All safety and efficacy analyses will be performed on the safety population.

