## **Safety Evaluations**

The Investigator will grade the ease of the procedure. Subjects will be monitored for approximately 1 hour immediately following injection.

Safety evaluations include:

 Adverse event reporting (Adverse Events will be assessed to determine if they are procedure related)

- Slit lamp biomicroscopy
- Gonioscopy
- Fundus exam
- Endothelial cell count with specular microscopy
- Pachymetry

Study Outcome Measure	
 
Anterior segment (AS)-OCT
 
Automatic Visual Field
 
Diurnal IOP (8 a.m., 10 a.m., 4 p.m.) will be checked at baseline, Day 14 (Visit 5), Day 42 (Visit 7), Day 85 (Visit 8), Month 4 (Visit 9), and Month 6 (Visit 11). IOP will continue to be measured if biological activity is noted at Month 6.
 
Intraocular pressure (at 8 a.m. on the day of insertion; Days 3, 7, and 28; and Month 5 [Visit 10])
 
	
Procedural Exclusion Criteria	Unsuccessful intracameral injection (record reason for injection failure on the electronic Case Report Form, i.e., eCRF); in the case of injection failure do not attempt another injection. The study will be supplemented with additional subjects to account for these subjects in order to ensure that the necessary number of subjects receive the implant to inform on safety, tolerability and efficacy.

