11.4. Demographics and Baseline Data

Subject disposition will be presented, including the number of subjects screened, enrolled and treated. The number of subjects who completed the study and reasons for discontinuation will be summarized.

Demographic and baseline characteristics (including disease and medical history) will be summarized.

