11.5. Safety Analyses

Safety will be assessed by adverse events, subject ocular comfort assessment, Investigator global tolerance score and other ocular-related outcomes.

Adverse events will be coded using Medical Dictionary for Regulatory Activities (MedDRA) by system organ class and preferred term. Separate summaries will be made for adverse events that are related to the injection procedure and the intracameral implant. In addition, serious adverse events will be summarized.

Summaries of other safety related outcomes will be provided.

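### The SAP 11.3 safety population covers only subjects who receive the implant, so procedure-related adverse events after a failed injection drop out of the SAP 11.5 summaries

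*SAP*

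**What the plan says.** SAP 11.3 defines one analysis set: "The safety population will consist of all subjects receiving the OTX-TIC implant". It then adds: "All safety and efficacy analyses will be performed on the safety population". No other set is named in the visible text.

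SAP 11.5 separates two sources of harm: "Separate summaries will be made for adverse events that are related to the injection procedure and the intracameral implant". It also plans a summary of serious adverse events.

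The protocol, in the procedural exclusion criteria that follow the Safety Evaluations list, anticipates failures and has the reason recorded: "Unsuccessful intracameral injection (record reason for injection failure on the electronic Case Report Form, i.e., eCRF". It continues: "in the case of injection failure do not attempt another injection". It then provides for replacement: "The study will be supplemented with additional subjects to account for these subjects". The stated purpose is that enough subjects receive the implant to inform on safety, tolerability and efficacy.

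The Safety Evaluations list says of adverse event reporting: "Adverse Events will be assessed to determine if they are procedure related". It does not limit this to successful injections.

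On disposition, SAP 11.4 says: "Subject disposition will be presented, including the number of subjects screened, enrolled and treated". Reasons for discontinuation are also summarised.

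**The concern.** Everyone in whom an injection is attempted is exposed to the risks of the procedure. SAP 11.3 selects the safety population by whether the procedure succeeded, and SAP 11.5 then describes procedural harm in that selected group. A subject who was injured during an attempt that delivered no implant is in neither the numerator nor the denominator.

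The event may well have been collected, since the protocol asks for procedure-relatedness to be assessed. The gap is in reporting. The disposition table may show that a failure occurred, but not what adverse events went with it.

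Safety and tolerability are stated objectives, and there are about 5 subjects per cohort. With so few subjects the descriptive counts are the result, and one omitted subject visibly changes a table.

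**Working it through.** **Plan's own figures.** There is no power or rate to reproduce: SAP 11.2 reports no formal sample size calculation. The one related count is consistent: 4 cohorts × about 5 = about 20 subjects.

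**Step 1: who is in the set.** The protocol uses receiving the implant to separate successful subjects from failures, because failures are replaced so that enough subjects receive it. SAP 11.3 uses the same verb to define the safety population. With no second attempt allowed, a failed subject cannot enter the set later. All safety analyses use this set, so the procedure-related and serious adverse event summaries in SAP 11.5 leave these subjects out.

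**Step 2: effect on a table.** Let *n* be the number implanted, *m* the number of failed attempts, and *e*₁ and *e*₂ the subjects with a procedure-related event in each group. The plan reports *e*₁/*n*; the rate in all attempts is (*e*₁ + *e*₂)/(*n* + *m*). The event counts are assumed. Exact (Clopper-Pearson) 95% intervals are in brackets.

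| Assumed situation, one failed attempt | Reported under SAP 11.3 | All attempts |
|---|---|---|
| Cohort of 5, no event in implanted, event in failed | 0/5 = 0% (0 to 52.2%) | 1/6 = 16.7% (0.4 to 64.1%) |
| Cohort of 5, one event in implanted, event in failed | 1/5 = 20.0% (0.5 to 71.6%) | 2/6 = 33.3% |
| Cohort of 5, one event in implanted, none in failed | 1/5 = 20.0% (0.5 to 71.6%) | 1/6 = 16.7% (0.4 to 64.1%) |
| All 20, one event in implanted, event in failed | 1/20 = 5.0% (0.1 to 24.9%) | 2/21 = 9.5% (1.2 to 30.4%) |
| All 20, one event in implanted, none in failed | 1/20 = 5.0% (0.1 to 24.9%) | 1/21 = 4.8% (0.1 to 23.8%) |

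**Step 3: direction and size in general.** Let *f* be the failure rate per attempt, *p* the event risk if implanted and *q* the event risk if the attempt fails. The all-attempts rate is (1 − *f*)*p* + *fq*. The reported rate is *p*, so reported minus all-attempts = *f*(*p* − *q*). The share of events omitted is *fq* / [(1 − *f*)*p* + *fq*]. With *p* = 10% assumed:

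| *f* | *q* | All-attempts rate | Reported minus all-attempts | Events omitted |
|---|---|---|---|---|
| 10% | 0% | 9.0% | +1.0 point | 0% |
| 10% | 10% | 10.0% | 0 | 10% (0.01/0.10) |
| 10% | 20% | 11.0% | −1.0 point | 18.2% |
| 10% | 50% | 14.0% | −4.0 points | 35.7% |
| 2% | 50% | 10.8% | −0.8 point | 9.3% |

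The count of events can only fall. The rate is understated if *q* > *p*, unchanged if *q* = *p*, and overstated if *q* < *p*. A higher risk in failed attempts is plausible, but the documents do not establish it.

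**Step 4: how likely the situation is.** The chance of at least one failure before *n* implants are placed is 1 − (1 − *f*)ⁿ.

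- For *n* = 20: 1 − 0.98²⁰ = 33%, 1 − 0.95²⁰ = 64%, 1 − 0.90²⁰ = 88%.
- For one cohort of 5: 1 − 0.95⁵ = 23%, 1 − 0.90⁵ = 41%.

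**The case against.** The strongest reply has four parts.

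- **Undefined terms.** Neither receiving the implant nor an unsuccessful injection is defined in the visible text. A misplaced, partly delivered or expelled implant could be counted as received, so omission is certain only where nothing was delivered. This stands, and it is a further reason to define the term.
- **Text not available.** SAP 11.1 refers to a general Statistical Plan that is not among the documents, some SAP text was not available, and SAP 11.6 and 11.7 are redacted. A listing of failed injections could be there. That cannot be excluded, but SAP 11.3 assigns every safety analysis to the implanted set and the visible text makes no exception.
- **Limited reach.** The objective concerns the drug product, which a population of recipients suits. Failure reasons go on the eCRF, and disposition shows enrolled against treated. Under the protocol's study design, opening Cohort 2 depends on the safety data of each Cohort 1 subject, and nothing visible ties that decision to the SAP 11.3 set. It is fair to confine the point to the procedure-related and serious adverse event summaries. But SAP 11.5 itself makes the procedure a separate source of harm, and none of these provisions reports the adverse events of failed-injection subjects.
- **Assumed rates.** Every failure and event rate above is assumed, and the bias in the rate can go either way. This is correct. The point rests on incomplete reporting of exposed subjects, not on a proven direction of bias.

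**Conclusion.** The concern holds and should be fixed. As written, SAP 11.3 excludes any subject in whom injection was attempted and no implant delivered, so the SAP 11.5 summaries of procedure-related and serious adverse events are incomplete whenever such a subject has an event. One such subject moves a cohort figure from 0/5 to 1/6 (16.7 percentage points) or a study figure from 1/20 to 2/21 (4.5 points). Over the assumed ranges *f* = 2% to 10%, *p* = 10% and *q* = 0% to 50%, the reported rate differs from the all-attempts rate by +1.0 to −4.0 points, and 0% to 36% of events are omitted. The upper end needs a 10% failure rate and a 50% event risk in failures together. If no injection fails, nothing is lost.

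**What to change.** In SAP 11.3, define the safety population as all subjects in whom intracameral injection of OTX-TIC was attempted, whether or not an implant was placed, and state that replaced subjects remain in it. Use it for procedure-related adverse events, serious adverse events and the injection failure rate. Keep implant recipients as a separate, named set for efficacy and implant-related summaries. Define receipt of the implant so that partial or misplaced delivery is classified in advance. State in the adverse event tables how long failed-injection subjects were followed.

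The cost is two or three sentences in the SAP and one extra denominator in the adverse event tables. The procedural event rate may look less favourable. The visible text sets no follow-up for failed-injection subjects, so their adverse event data may be shorter or incomplete; the tables should say so.

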11.4. Demographics and Baseline Data

Subject disposition will be presented, including the number of subjects screened, enrolled and treated. The number of subjects who completed the study and reasons for discontinuation will be summarized.

Demographic and baseline characteristics (including disease and medical history) will be summarized.

11.5. Safety Analyses

Safety will be assessed by adverse events, subject ocular comfort assessment, Investigator global tolerance score and other ocular-related outcomes.

Adverse events will be coded using Medical Dictionary for Regulatory Activities (MedDRA) by system organ class and preferred term. Separate summaries will be made for adverse events that are related to the injection procedure and the intracameral implant. In addition, serious adverse events will be summarized.

Summaries of other safety related outcomes will be provided.

11.6. Efficacy Analyses

A large rectangular area of the page is completely blacked out, indicating that the content for the Efficacy Analyses section has been redacted.

11.7. Exploratory Analyses

A large rectangular area of the page is completely blacked out, indicating that the content for the Exploratory Analyses section has been redacted.
